3'-Deoxy-3'-[¹⁸F]fluorothymidine ([¹⁸F]FLT) is a structural analog of the DNA constituent, thymidine (Figure 6.iii.2). It is a radiolabeled imaging agent that has been proposed for investigating cellular proliferation with positron emission tomography (PET). Although [¹⁸F]FLT is not incorporated into DNA, it is trapped in the cell due to phosphorylation by *thymidine kinase 1*, a part of the salvage pathway. As such, it has potential as a marker of proliferating tumor in proportion to the DNA synthesis rate. Therefore, [¹⁸F]FLT is proposed as a radiolabeled imaging probe for *in vivo* assessment of cellular proliferation in malignant tumors using PET. For complete information, please refer to the Investigator's Brochure: "3'-deoxy-3'-fluorothymidine: [¹⁸F]FLT, An Investigational Positron Emission Tomography (PET) Radiopharmaceutical for Injection and intended for use as an *in vivo* diagnostic for imaging active cellular proliferation of malignant tumors."

6.iii.3.c. Rationale

[¹⁸F]FLT is a radiolabeled imaging probe for *in vivo* assessment of cellular proliferation using PET. Preclinical and clinical studies suggest that early imaging of response using this radiopharmaceutical can demonstrate effectiveness of treatment in a variety of tumors. In this protocol, we will assess regional FLT uptake in patients with malignant brain tumors.

[figure not shown]

Figure 6.iii.2. Molecular structures for FLT and thymidine

Specifically, we propose to use [¹⁸F]FLT PET/CT to assess changes in imaging measures in the clinical course of brain tumor patients. Subsequent studies (not part of this trial) could eventually allow treatments to be tailored to the tumor response measured by imaging, eliminating the use, costs and toxicity of ineffective treatments and improving the patient's quality of life. This is our long-term objective. In this protocol, FLT PET/CT imaging measures will be compared with clinical measures of tumor response to test specific hypotheses.

Hypotheses for this protocol.

1. Quantifying tumor proliferation in brain tumors will provide a reliable measure of disease. For example, kinetic analysis of the FLT-PET/CT data will allow distinction between true progression and pseudo-progression in patients with glioblastoma who have finished surgery plus radiotherapy and temozolomide and whose measurable disease by standard MRI after initial treatment has appeared to progress.

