2. Changes in tumor proliferation (FLT flux) as determined by kinetic analysis of FLT-PET/CT imaging will correlate with clinical treatment response.
3. Brain tumor cellular proliferation is heterogeneous. This heterogeneity can be quantified by the FLT PET/CT procedure and is an independent predictor of response.

6.iii.4. PARTICIPANT SELECTION

6.iii.4.a. Inclusion Criteria:

- 6.iii.4.a.1. At least 18 years of age.
- 6.iii.4.a.2. Have a diagnosis or suspected diagnoses of a brain tumor (primary, recurrent, or metastatic) by standard clinical diagnosis such as pathology or imaging.
- 6.iii.4.a.3. Planned for treatment with radiation, chemotherapy and surgical resection or any of these treatment strategies combined. The clinical treatment will not be influenced by the experimental imaging studies described in this protocol.

6.iii.4.b. Exclusion Criteria:

- 6.iii.4.b.1. Inability to provide informed consent
- 6.iii.4.b.2. Pregnancy
- 6.iii.4.b.3. Inability to lie still for the imaging study
- 6.iii.4.b.4. Weight over 350 lbs., the weight limit of the tomograph table.

6.iii.4.c. Inclusion of Women and Minorities

Patients 18 years of age or older with a brain tumor and planning to undergo therapy will be eligible for study participation.

No other discriminatory factors, including age, sex, or ethnic background will be used to determine eligibility. Every effort will be made to ensure that minorities are recruited for study participation.

6.iii.4.d. Accrual Targets

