The analysis of data for these hypotheses involves within-subject changes where the variance in values will be less than between-subject FLT results that we have published. Furthermore, this power analysis has assumed that only data from a single volume of interest (VOI) for each subject will be used. In the context of our aims, this could be considered inefficient. In many subjects it will be possible to include data from spatially well-separated and hence substantially uncorrelated sub-regions within large tumors (Spence, 1998) as distinct sampling units for consideration with this hypothesis. Notwithstanding the additional variability that sub-region measurements will have, it is likely that some gains in statistical precision can be realized by this approach. Thus the 90% power estimate is conservative.

Hypothesis 1. Among GBM patients identified as progressing according to Macdonald criteria at 1-month follow-up, the mean FLT flux in true progression cases will be compared to the corresponding mean in the pseudo-progression cases. Preliminary data indicate that 40% of MRI diagnosed progression can be expected to be pseudo-progression. Our data on recurrence vs radionecrosis for KFLT recurrences showed a mean of 0.017 and a standard deviation of 0.005 (Spence, 2006). The mean of the radionecrosis group was 0.004, roughly one-quarter for that for recurrences. Thus, conservatively, assuming that pseudo-progressors showed even a 30% increase over the mean KFLT value, the expected difference between the groups would be 0.017×0.3 or about 0.005. From this, the expected standardized effect is 0.99. Using a 2-sample t-test with significance level of 5% for assessment of the hypothesis, the power of our study is about 95%.

6.iii.14.c. Analysis Plan

Percentage change between pre-treatment and post-therapy measurements will be computed for [¹⁸F]FLT PET/CT measures of transport, K₁, and flux (KFLT). Log transformations will be considered if the rates of change are highly skewed. Outcome analysis studies are directed toward predicting tumor response. In the case of progression, a multivariate logistic regression will be used to produce an analysis of how the combination of standard diagnostics plus the FLT parameters (K₁, KFLT, SUVmean) obtained shortly after therapy can best be combined to

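### The 95% power claimed for Hypothesis 1 is out of reach: it needs about 58 progressing glioblastoma patients, and the study enrols at most 40 patients of any tumor type

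*Combined protocol and SAP*

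**What the plan says.** Section 6.iii.14.b gives a separate power statement for Hypothesis 1. The comparison is of mean FLT flux (KFLT) between true progression and pseudo-progression, and it is restricted: "Among GBM patients identified as progressing" by Macdonald criteria at one month. On the split between the groups it says "Preliminary data indicate that 40% of MRI diagnosed progression can be expected to be pseudo-progression".

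The effect is built from earlier data in which recurrences had mean KFLT 0.017 and SD 0.005. On the comparison group in those data the plan says "The mean of the radionecrosis group was 0.004, roughly one-quarter for that for recurrences". It then takes a smaller difference as a conservative choice, "assuming that pseudo-progressors showed even a 30% increase over the mean KFLT value", which gives 0.017 × 0.3, or about 0.005. It continues "From this, the expected standardized effect is 0.99", and concludes: "Using a 2-sample t-test with significance level of 5% for assessment of the hypothesis, the power of our study is about 95" per cent.

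No number of patients is attached to this calculation, and the sidedness of the test is not stated. The only sizes in the document are the target of 30 patients (6.iii.4.d and 6.iii.14.a) and the maximum enrolment of 40 (6.iii.4.d).

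Hypothesis 1 in section 6.iii.3.c concerns glioblastoma patients who have finished surgery, radiotherapy and temozolomide and "whose measurable disease by standard MRI after initial treatment has appeared to progress". Eligibility is much wider. Section 6.iii.4.a asks only that patients "Have a diagnosis or suspected diagnoses of a brain tumor (primary, recurrent, or metastatic").

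**The concern.** A power figure needs an effect, a significance level, a sidedness and a sample size. Two of these four are missing, so the 95% can be checked only against the sizes the study could reach. An effect of about one standard deviation needs more than 50 patients for 95% power in a two-sided comparison, and this study stops at 40. The comparison also uses only a subset of those enrolled.

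Section 6.iii.3.a names the distinction between progression and pseudo-progression as the primary hypothesis, and the schema says promising results will be used to design larger trials. A reader told that power is 95% will take a non-significant result as fairly strong evidence that FLT flux does not separate the groups, since the implied chance of missing the assumed difference is 5%. If the true chance is several times larger, a null result carries far less information than the plan implies.

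**Working it through.** **Inputs, all from 6.iii.14.b unless noted**

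- Two-sample t-test, 5% level, sidedness not stated (both are computed).
- Standardized effect d = 0.99.
- 40% pseudo-progression, 60% true progression.
- Study size 30 (6.iii.4.d, 6.iii.14.a), maximum 40 (6.iii.4.d).

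**The effect size.** 0.017 × 0.3 = 0.0051, and 0.0051 / 0.005 = 1.02. The printed 0.99 is compatible with this if the SD was rounded (0.0051 / 0.99 = 0.00515). The check uses 0.99 and notes where 1.02 would matter.

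**Formula.** Exact power from the noncentral t distribution, with noncentrality δ = d × √(n₁n₂/(n₁+n₂)) and n₁+n₂−2 degrees of freedom.

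**Attempt to reproduce 95%, counting every enrolled patient as a progressing glioblastoma case**

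- N = 30 (12 vs 18): δ = 0.99 × √(216/30) = 0.99 × 2.683 = 2.66, 28 df.
- N = 40 (16 vs 24): δ = 0.99 × √(384/40) = 0.99 × 3.098 = 3.07, 38 df.

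| Total | Split | d | Two-sided | One-sided |
|---|---|---|---|---|
| 30 | 12/18 | 0.99 | 72.7% | 82.8% |
| 40 | 16/24 | 0.99 | 84.8% | 91.4% |
| 30 | 12/18 | 1.02 | 75.2% | 84.7% |
| 40 | 16/24 | 1.02 | 86.9% | 92.8% |
| 40 | 20/20 | 1.02 | 88.2% | 93.6% |

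None reaches 95%. The last row drops the plan's own 40/60 split.

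**Smallest total that reaches 95%**

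| Split | d | Two-sided | One-sided |
|---|---|---|---|
| 40/60 | 0.99 | 58 | 48 |
| 40/60 | 1.02 | 54 | 45 |
| 1:1 | 0.99 | 56 | 46 |
| 1:1 | 1.02 | 52 | 44 |

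For the first entry, 23 vs 35 gives δ = 0.99 × √(805/58) = 3.69 with 56 df and power 95.2%. Every entry exceeds 40. Thirty per group (60 in all) would give 96.5% two-sided; whether the stated figure arose that way cannot be told from the document.

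**A more realistic number of progressors (scenario only).** Assume every patient has glioblastoma and that the 30–50% early treatment failure rate in 6.iii.3.a applies to progression at one month. That gives 0.3 × 30 = 9 to 0.5 × 30 = 15 progressors, or 0.3 × 40 = 12 to 0.5 × 40 = 20. At d = 0.99:

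| Progressors | Split | Two-sided | One-sided |
|---|---|---|---|
| 9 | 4/5 | 25% | 38% |
| 12 | 5/7 | 33% | 47% |
| 15 | 6/9 | 41% | 55% |
| 20 | 8/12 | 54% | 67% |

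Enrolling patients with other tumors lowers these counts further.

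**The case against.** **The effect is deliberately conservative.** The earlier means give (0.017 − 0.004) / 0.005 = 2.6, assuming the same SD in both groups. At that effect two-sided power is 94% with 10 progressors (4/6) and 98% with 12 (5/7). So the study could be well powered if pseudo-progression behaves like radionecrosis. This stands as a statement about a larger effect. It does not support the printed figure, because the plan sets that effect aside and attaches its 95% to 0.99.

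**Under the loosest reading the gap is small.** One-sided, 20 vs 20, d = 1.02 gives 93.6%, or 94.3% by the normal approximation. That is close to 95%, but only if all 40 enrolled patients are progressing glioblastoma cases and the 40/60 split is abandoned. The wide eligibility makes the first condition unrealistic.

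**Sub-regions could serve as extra sampling units.** Section 6.iii.14.b makes this argument just before Hypothesis 1, and one phrase refers to a single hypothesis, so there is some ambiguity. The paragraph nevertheless opens on the survival hypotheses (2 and 3) and closes on a 90% power figure, not the 95%. It supplies no sample size for Hypothesis 1.

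**The plan already warns of limited power.** Section 6.iii.4.d says the funding limit on accrual will affect power, and 6.iii.14.c says the logistic and ROC analysis may be underpowered. The first is general and the second concerns another analysis. Neither withdraws the 95%.

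**This is a pilot, and the hypothesis may not be primary.** Section 6.iii.3.c introduces pseudo-progression as an example, and no specific aim names it. That tempers the consequences, and FLT results do not direct treatment. A pilot need not have 95% power, but it should not claim power it lacks.

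**Conclusion.** The concern holds. At the plan's own effect (0.99), level and 40/60 split, power cannot exceed 85% two-sided or 91% one-sided, even if all 40 permitted patients were progressing glioblastoma cases. At the 30-patient target the ceilings are 73% and 83%. The chance of missing the assumed difference is therefore at least 15–27% two-sided (9–17% one-sided) at these ceilings, against the 5% implied. In the 30–50% progression scenario it is 46–75% two-sided.

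The conclusion does not depend on sidedness, on 0.99 versus 1.02, or on equal versus 40/60 groups: all three at their most favourable still require 44 patients. It is conditional on an effect of about one SD, which is the effect the plan chose. The 25–54% scenario range is softer, since it assumes an all-glioblastoma sample and equates early treatment failure with progression at one month. The finding rests on the ceilings alone.

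A smaller point is the direction of the assumed effect. The plan posits higher flux in pseudo-progressors, while the radionecrosis data it cites show lower flux. This does not change two-sided power, but it matters if a one-sided test is intended.

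**What to change.** In 6.iii.14.b, under Hypothesis 1:

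1. State the expected number of scanned glioblastoma patients who will meet the progression definition, and how it follows from total enrolment.
2. State whether the test is one- or two-sided.
3. Replace the 95% with the power at that number. Two-sided, d = 0.99, 40/60: 25% with 9 progressors, 33% with 12, 41% with 15, 54% with 20, 73% with 30, 85% with 40.
4. Alternatively, give the detectable difference (two-sided, SD 0.005 in both groups). With 12 progressors (5/7) it is 1.82 SD (1.82 × 0.005 = 0.009) for 80% power and 2.35 SD (0.012) for 95%. With 20 (8/12) it is 1.35 SD (0.007) and 1.74 SD (0.009). This suits a pilot, because these values can be set beside the 0.013 difference in the earlier data.
5. Reconcile the assumed increase in pseudo-progressors with the lower radionecrosis mean.

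The cost is wording and one recalculated figure. The stated power becomes less favourable, but no patients are added and conduct does not change.

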Standard initial treatment for glioblastoma currently consists of surgical removal of as much of the MRI contrast-enhancing lesion as can be accomplished safely, followed by radiotherapy and temozolomide (TMZ) chemotherapy for 6 weeks. Unfortunately, early treatment failures occur in 30-50% of patients. This definition of treatment failure is described as an increase in the MRI T1+Gd tumor volume (de Wit, 2004). Immediate post-radiotherapy MRI changes in malignant glioma can mimic tumor progression (Taal, 2008). The incidence of this pseudo-progression in a cohort of malignant glioma patients treated with chemo-radiation with temozolomide is significant (Brandes, 2008). From 28-52% of these patients will demonstrate improvement on subsequent MRI studies when they continue on standard TMZ chemotherapy. This situation defines pseudo-progression as opposed to true disease progression, where continued treatment with temozolomide is associated with continued clinical decline and MRI T1+Gd worsening. Clinicians armed with anatomic MRI imaging alone may wrongly conclude that standard treatment is failing in these patients, leading to cessation of a treatment that is actually working. Also, misdiagnosing pseudo-progression in patients who are responding could risk entering such patients into phase II or III trials of new agents, decreasing the statistical power of the study and potentially leading to falsely positive outcomes. On the other hand, continuing TMZ in the patients that are true progressors wastes their time and physiological resources when they should be offered second line treatment or enrollment in a phase II or III research treatment protocol. Thus, the ability to make the important distinction between progression and pseudo-progression is critical for the care of treated brain tumor patients and could potentially change patient management. In some patients, the neuropathologist who reviews the resected tumor resolves the question of pseudo-progression versus true progression. Ideally, however, noninvasive imaging methods should be developed to answer this question reliably. Our primary hypothesis is that FLT PET/CT should be able to distinguish between when the patient has true tumor progression and needs to change therapy and when the MRI contrast is reflecting pseudo-progression and the patient should continue with TMZ chemotherapy. That way, the 50% or possibly more true progressors could avoid continuing futile TMZ.

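### Hypothesis 1 is about telling true from pseudo-progression in a patient, but is assessed by a t-test of group means, with no accuracy estimate for FLT flux tied to it

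*Combined protocol and SAP*

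**What the plan says.** Section 6.iii.3.a (Study Disease) puts the aim at the level of the patient and the treatment decision: "Our primary hypothesis is that FLT PET/CT should be able to distinguish between when the patient has true tumor progression and needs to change therapy", as against pseudo-progression, where standard chemotherapy continues. Hypothesis 1 in 6.iii.3.c (Rationale) says that "kinetic analysis of the FLT-PET/CT data will allow distinction between true progression and pseudo-progression in patients with glioblastoma" who appear to progress on MRI after initial treatment.

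Section 6.iii.14.b (Power Calculations, Hypothesis 1) turns this into a comparison of averages: "the mean FLT flux in true progression cases will be compared to the corresponding mean in the pseudo-progression cases". The test is given as "Using a 2-sample t-test with significance level of 5% for assessment of the hypothesis". For planning, KFLT in recurrences "showed a mean of 0.017 and a standard deviation of 0.005", the radionecrosis mean was 0.004, and the difference is obtained by "assuming that pseudo-progressors showed even a 30% increase over the mean KFLT value". This leads to the statement that "the expected standardized effect is 0.99", with power of about 95%. Pseudo-progression is expected in 40% of MRI-diagnosed progressions.

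Section 6.iii.14.c (Analysis Plan) adds a multivariate logistic regression for progression that combines standard diagnostics with K1, KFLT and SUVmean measured shortly after therapy, and an ROC description of the resulting prognostic variable. It gives no performance target and does not mention Hypothesis 1.

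**The concern.** The claim and its test answer different questions. A t-test asks whether two averages differ. Whether FLT can distinguish depends on how far the two distributions overlap, which is what AUC, sensitivity and specificity describe. A marker with heavy overlap and one with little overlap can both return p<0.05.

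The study is meant to supply preliminary data for larger trials. If the Hypothesis 1 result is a p-value, the study could report that FLT distinguishes the two conditions without giving the figure a follow-on diagnostic study most needs: how well KFLT separates them, and with what uncertainty.

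The direction of a successful result is also unclear. The cited means put the non-tumour condition well below recurrence, while the planning sentence makes pseudo-progressors 30% higher.

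**Working it through.** **Inputs, all from 6.iii.14.b unless noted.** Recurrence mean 0.017, SD 0.005; radionecrosis mean 0.004; 30% relative difference; standardized effect d = 0.99; 40% pseudo-progression; 5% level. Thirty patients (stated there for hypotheses 2 and 3; no number is given for Hypothesis 1). Enrolment up to 40 (6.iii.4.d). Early failure in 30-50% of patients (6.iii.3.a).

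**Assumptions.** Normal distributions with a common SD of 0.005. The plan gives no SD for pseudo-progression.

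**The plan's own figures.** 0.017 × 0.3 = 0.0051, and 0.0051/0.005 = 1.02; with the difference rounded to 0.005 it is 1.00. The stated 0.99 is close. The stated power of about 95% is not reproduced at d = 0.99: by the noncentral t, 18 true vs 12 pseudo gives 72.7% two-sided or 82.8% one-sided; 24 vs 16 gives 84.8% or 91.4%. That is a separate matter; the point here does not depend on it.

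**Discrimination at the planned effect, d = 0.99.**
- AUC = Φ(d/√2) = Φ(0.700) = 0.758.
- Misclassified at the midpoint cut = Φ(−d/2) = Φ(−0.495) = 31.0%.
- Misclassified at the cut that minimises error with 40% pseudo-progression: 29.6%, made up of 18.3% of true progressors and 46.6% of pseudo-progressors (0.6 × 0.183 + 0.4 × 0.466 = 0.296).
- Specificity at 90% sensitivity = Φ(0.99 − 1.2816) = 38.5%.

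**For contrast.** If pseudo-progressors resembled radionecrosis, d = (0.017 − 0.004)/0.005 = 2.6, AUC = 0.967, and 9.7% are misclassified at the midpoint. The t-test has one pass mark for both situations.

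**Smallest observed effect that is significant**, if the test is two-sided: d = t(0.975, N − 2) × √(1/n₁ + 1/n₂).

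| True vs pseudo | d needed | Misclassified at midpoint |
|---|---|---|
| 24 vs 16 | 0.653 | 37.2% |
| 18 vs 12 | 0.763 | 35.1% |
| 9 vs 6 | 1.139 | 28.5% |
| 5 vs 4 | 1.586 | 21.4% |

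The last two rows follow from the plan's early-failure rate: 30% to 50% of 30 is 9 to 15 progressors, before allowing for enrolled patients who do not have glioblastoma.

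**Precision of an AUC at 0.758** (Hanley-McNeil): SE² = [A(1 − A) + (n₁ − 1)(a − A²) + (n₂ − 1)(b − A²)]/(n₁n₂), with a = A/(2 − A) = 0.610, b = 2A²/(1 + A) = 0.654 and A² = 0.575. For 18 vs 12: (0.183 + 17 × 0.0357 + 11 × 0.0791)/216 = 0.0077, so SE = 0.088 and the half-width is 1.96 × 0.088 = 0.17. For 24 vs 16 it is 0.15; for 9 vs 6, 0.25.

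**A fixed cut from the plan's data.** The midpoint (0.017 + 0.004)/2 = 0.0105 gives sensitivity Φ(1.3) = 90%. With a pseudo-progression mean of 0.7 × 0.017 = 0.0119, specificity is Φ(−0.28) = 39%.

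**The case against.** The strongest reply is that patient-level discrimination is already planned. Section 6.iii.14.c promises an individual probability and an ROC curve, and neither statement of the hypothesis says KFLT alone. So a reader who infers that the plan contains no patient-level analysis would be wrong. What remains is narrower. That ROC belongs to a fitted combination that includes standard diagnostics, no validation step is described, and nothing connects it to the conclusion on Hypothesis 1. A score fitted and judged on the same few patients will tend to look better than it is, and it does not show what the flux measure named in the t-test achieves.

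A reader might also infer that the test is two-sided and passes with a third of patients misclassified. The documents support neither as a general statement. Sidedness is not given. The 35% and 37% figures need 30 or 40 evaluable progressors; with 9 to 15, significance requires a larger observed effect, corresponding to 21% to 28%.

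Nor would an AUC be a stricter hurdle in itself. An interval that merely excludes 0.5 needs an AUC of about 0.69 at 18 vs 12 and 0.67 at 24 vs 16, close to the 0.71 and 0.68 implied by two-sided significance. The gain is in reporting accuracy with its uncertainty, not in a new pass mark.

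Finally, this is a pilot, FLT does not direct therapy, and 6.iii.14.c admits low power. That limits the consequence. It does not make a p-value the more useful output for planning the next study.

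**Conclusion.** The point holds in this form: a patient-level discrimination hypothesis is formally assessed by a difference in means, and no accuracy estimate for KFLT is tied to it. At the effect the plan itself assumes, the AUC is 0.76 and about 30% of patients are misclassified (29.6% at the best cut, 31.0% at the midpoint). These figures rest on normality and an SD of 0.005 in both groups; a pseudo-progression mean near the radionecrosis value would give much better separation.

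The 30% increase runs against the cited means of 0.004 and 0.017. It is an error of direction only: the size of the difference, and hence two-sided power, is unchanged.

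**What to change.** In 6.iii.14.b and 6.iii.14.c:

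1. For Hypothesis 1, report the nonparametric AUC of post-therapy KFLT alone with a 95% confidence interval, fixing the direction as true progression higher. Keep the t-test alongside it and state its sidedness.
2. Say that any statement that FLT distinguishes the two conditions will rest on the AUC estimate and its lower limit, not on p<0.05.
3. Optionally add sensitivity and specificity with exact intervals at a cut fixed in advance, as description only. The value 0.0105 is provisional: it derives from radionecrosis, not pseudo-progression, and gives about 39% specificity under the plan's own assumed difference.
4. Change the planning sentence to a 30% lower mean in pseudo-progressors.

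The cost is wording. KFLT and the true/pseudo classification are already needed for the t-test, so no extra scans or patients are required. The Study Calendar marks the post-therapy scan as optional, so the number available should be reported. The drawback is a wide interval in place of a p-value: half-width about 0.17 with 30 progressors, 0.15 with 40 and 0.25 with 15. With 9 vs 6, the approximate interval around 0.758 runs from 0.51 to the upper bound of 1.
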